3.1 General

3.1.1 Estimands and Censoring Scheme

Summaries of the descriptions of the estimand attributes and censoring schemes are shown in **Table 3**. Like TACT, the primary analysis will include all identified events obtained as part of the planned follow-up from infusion visits and call center interviews.

Table 3. Key Study Estimands and Censoring Scheme.

Objective Description / Study Population	Endpoint	Summary statistics	Events to be included in the endpoint derivation	Censoring date
Primary Objective/ mITT	Time from randomization to the first occurrence of primary composite endpoint of all-cause mortality, MI, stroke, coronary revascularization, or hospitalization for unstable angina	Hazard ratio estimate based on a Cox proportional hazards model.	All positively adjudicated primary endpoint events post-randomization except those occurring after withdrawal of consent or ICF expiration. Events occurring after withdrawal consent or ICF expiration will be censored. Subjects with events after withdrawal or ICF expiration will be censored at the min(date withdrew consent, date of last contact with patient/proxy where event status was assessed).	Among subjects not experiencing endpoint of interest: Censoring date = min(date withdrew consent, date of last contact with patient/proxy where event status was assessed) Date of last contact defined as: If the last contact occurred during the study infusion phase - use last infusion visit date where survival status and event status were assessed (yes or no to event). If last contact occurred during call center follow up period – use ‘complete’/‘incomplete’ status date by patient/proxy where survival status and hospitalization status were assessed (yes or no to hospitalization).

				For composite endpoints, date of last assessment = the earliest of the last assessment date among all components.
Secondary Objective / mITT	Overall rate of recurrent events due to all-cause mortality, MI, stroke, coronary revascularization, or hospitalization for unstable angina	Hazard ratio estimate based on a proportional intensity model by Andersen-Gill and a marginal model by Wei, Lin and Weissfeld.	*same as primary endpoint	*same as primary endpoint
Secondary Objective / mITT	Time from randomization to the first occurrence of the secondary composite endpoint of cardiovascular mortality, MI, or stroke	Cause specific hazard ratio estimate based on a cause-specific Cox proportional hazards model.	All positively adjudicated endpoint events post-randomization except those occurring after withdrawal of consent or ICF expiration date. Non-CV death or undetermined cause of death is considered a competing risk. Among subjects experiencing competing risk (non-CV death or undetermined death is a competing risk of CV death or MI/stroke if a subject died without having any	Among subjects not experiencing endpoint of interest or competing event: Censoring date = min(date withdraw consent, date of last contact with patient/proxy where event status was assessed) *Date of last contact defined in 1 st row, 5 th column (primary endpoint)

			
of these events beforehand):
 
Event date = non-CV or undetermined death date;
	
Secondary Objective / mITT	Time from randomization to all-cause mortality	Hazard ratio estimate based on a Cox proportional hazards model.	
All deaths post-randomization (including adjudicated deaths obtained from the NDI search)
 
A death date after withdrawn consent or ICF expiration (obtained from public data source) is considered an event.
	
Among subjects who are alive:
 
Censoring date = (date last known alive)
 
Date of last known alive defined as:
 
If the last contact occurred during the study infusion phase - use last infusion visit date.
 
If last contact occurred during call center follow up period – use ‘complete’/‘incomplete’ status date by patient/proxy or (‘not done’ status date where source = patient) or last alive date from Call Center where death status was assessed.

Secondary Objective / mITT	Total number of SAE and percentage of patients experiencing at least 1 SAE.	Number and proportions by treatment group. Confidence intervals will be based on the Miettinen-Nurminen method.	Randomization to min(withdraw consent, 30 days post final infusion)	N/A

Sensitivity Analysis of the Primary Outcome / Bayesian analysis using TACT results as one of the priors / mITT	*Same as primary analysis	Treatment effect mean posterior hazard ratio based on a Bayesian time to event model	*Same as primary analysis	*Same as primary analysis
Sensitivity Analysis of the Secondary All-Cause Mortality Outcome / Bayesian analysis using TACT results as one of the priors / mITT	*Same as primary analysis	Treatment effect mean posterior hazard ratio based on a Bayesian time to event model	*Same as primary analysis	*Same as primary analysis
Sensitivity Analysis of the Primary Outcome / ITT	*Same as primary analysis	*Same as primary analysis	*Same as primary analysis	*Same as primary analysis
Sensitivity Analysis of the Primary Outcome / mITT with imputed event status for subjects withdrew /lost to follow up	*Same as primary analysis	*Same as primary analysis	*Same as primary analysis except that the event status will be imputed for subjects who withdrew consent or lost to follow up before study completion	*Same as primary analysis

Sensitivity Analysis of the Primary Outcome/ mITT with the exclusion of positively adjudicated events > 1 year after the last contact where all components of the composite were assessed
	
*Same as primary analysis
	
*Same as primary analysis
	
*Same as primary analysis but exclude positively adjudicated events more than 1 year from the most recent study contact where all components of the composite endpoint were assessed.
	
Among subjects not experiencing endpoint of interest or experiencing first CEC event > 1 year after event assessment date: Censoring date = min(date withdraw consent, date of last contact with patient/proxy where event status was assessed)
 
*Date of last contact defined in 1st row, 5th column (primary endpoint)

Sensitivity Analysis of the Secondary Composite Outcome/ Where undetermined death is considered CV-death / mITT
	
*same as secondary composite endpoint
	
*same as secondary composite endpoint, where: Undetermined death is analyzed as CV-death.
	
*same as secondary composite endpoint
	
*same as secondary composite endpoint

Sensitivity Analysis of the Secondary Composite Objective / Cause of death based on best available data (from CEC or CRF if CEC is unavailable) / mITT
	
*Same as secondary composite analysis
	
*Same as secondary composite analysis
	
*Same as secondary composite analysis, where: Cause of death is determined based on best available data. If cause of death from CEC is available, use CEC cause of death. Otherwise, if CRF cause of death available, use CRF cause of death.
	
*Same as secondary composite analysis

			If cause of death is unavailable in CEC and CRF, use NDI cause of death.	
Sensitivity Analysis of the Secondary All-Cause Mortality Outcome / Censor at the date of NDI assessment / mITT	*Same as secondary all-cause mortality analysis	*Same as secondary all-cause mortality analysis	*Same as secondary all-cause mortality analysis	Among subjects who are alive: Censoring date = max(date of NDI assessment, last known alive date) Date of NDI assessment is defined as: The last date that NDI results were assessed. This will be consistent for all participants without an event.

*See section 2.1 for the definition of ITT and mITT.

One participant who was randomized twice and received infusions from the second site will be censored at the second randomization. The other participant who was lost to follow-up at the first site and then was randomized at the second site will be censored at the time of lost to follow-up at the first site.

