Another sensitivity analysis is planned to assess how the primary analysis would be affected by various assumptions regarding the occurrence of primary endpoint events among those who withdrew consent or were lost to follow-up, as was performed and published in TACT. Baseline characteristics by treatment group will be assessed for the patients who did versus did not withdraw consent or were lost to follow-up. Events will be imputed by simulation only for the consent withdrawal or lost patients who did not have a documented occurrence of one of the primary events prior to the withdrawn consent/lost to follow-up. The different percentages of the withdrawn or lost patients will be assumed to have an event at their censoring time. The event rates among patients that withdrew or were lost to follow-up in each treatment group will be varied across a broad spectrum and include scenarios that were markedly unfavorable to chelation. The imputed event rates for patients who withdrew consent or were lost to follow-up will be combined with the observed event rates of patients who completed the study to assess the treatment effect via a hazard ratio. These analyses will focus on scenarios in which events among withdrawn or lost patients in the active arm are assumed to occur at a higher rate than withdrawn or lost patients in the placebo arm.

Another sensitivity analysis is planned for the primary endpoint to censor, at the point of last contact, those deaths that were identified more than one year following the most recent study contact.

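### SAP Table 3 sets different cut-offs for counting events and for censoring in the primary analysis, and the one-year sensitivity analysis is defined in two ways

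*SAP*

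**What the plan says.** All of this is in the SAP.

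- **Which events count (Table 3, primary row).** "All positively adjudicated primary endpoint events post-randomization except those occurring after withdrawal of consent or ICF expiration". Being after last contact is not a ground for exclusion.
- **Censoring of event-free patients (same row).** "Censoring date = min(date withdrew consent, date of last contact with patient/proxy where event status was assessed"). For composites the date can be earlier still: "For composite endpoints, date of last assessment = the earliest of the last assessment date among all components".
- **Patients whose event is excluded (same row).** "Subjects with events after withdrawal or ICF expiration will be censored at the min(date withdrew consent, date of last contact with patient/proxy" where status was assessed). ICF expiration is in neither minimum.
- **Opening sentence of 3.1.1.** "the primary analysis will include all identified events obtained as part of the planned follow-up from infusion visits and call center interviews". This is narrower than the event column.
- **One-year sensitivity analysis, Table 3.** "exclude positively adjudicated events more than 1 year from the most recent study contact where all components of the composite endpoint were assessed".
- **One-year sensitivity analysis, 3.2.2.** It censors at last contact "those deaths that were identified more than one year following the most recent study contact".

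The recurrent-event row of Table 3 takes over the primary rules, and the row for the secondary composite has the same structure.

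**The concern.** A hazard is events divided by time at risk, so both need the same cut-off. Here they differ in two places, with opposite effects.

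After ICF expiration no event can count, but event-free time still can. A patient whose event is excluded for this reason can also be carried as event-free up to a contact that came after the event. Both lower the rate.

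After last contact an adjudicated event can count, but patients without one have left the risk set. Time after loss is then counted only for patients who have an event, which raises the rate. If one arm loses more patients, that arm gains more events without the matching time, and the hazard ratio moves.

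The analysis that should show how much late events matter is written in two incompatible ways, so two programmers could build different datasets from the same SAP. The primary comparison also opens the testing hierarchy in 3.2.1, so its dataset should be fixed without ambiguity.

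**Working it through.** **1. ICF expiration.** Consent precedes randomization (Protocol 11.2). Screening is to be completed within 30 days of consent, after which the screening labs must be redrawn (Protocol 6.2.1). SAP Appendix I counts expiration as five years from initial consent, without re-consent. SAP 1.1 counts follow-up from randomization, with the last call at month 60. With a 30-day screening period:

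- expiration = randomization − 30 days + 5 years
- on-schedule month-60 call = randomization + 5 years
- gap = 30 days at risk in which no event can count

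A late call or a longer screening period lengthens the gap. Only patients who reach five years before the administrative end of June 30, 2023 (SAP 2.4) are affected, that is, those who consented by about mid-2018.

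**2. Do events after last contact count?** The event column does not exclude them. The Table 3 row that removes events more than a year after last contact is needed only if the primary analysis includes them. SAP 2.2 gives a route: National Death Index (NDI) leads with supporting documents go to the events committee and are then used in the analysis. Against this stands the opening sentence of 3.1.1. The likelier reading is that they count, but the SAP does not settle it.

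**3. Check against the plan's own figures.** Required events = 4(1.960 + 1.036)² / (ln 0.70)² = 4 × 8.978 / 0.1272 = 282.3, against the stated 282. A simulation of SAP Table 2 used 500 per arm, 10.4 and 7.28 events per 100 patient-years, enrolment assumed uniform over 4.25 years, at least 2.5 years of follow-up and a five-year cap. For overall dropout of 5/7/10% it gave 303/300/296 events (SAP: 299/295/288) and 87.3/87.7/86.7% power (SAP: 89/88/87%). This is close enough to use as a base.

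**4. Size of the asymmetry.** Loss by arm and the share *f* of post-contact events later found are assumptions; *f* runs from 0.3 to 1.0. Each entry is the mean HR from a two-group unadjusted Cox model (1,200 replicates). Single cut-off means that everyone is censored at last contact.

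| Loss active / placebo | True HR | Single cut-off | SAP rule, f = 0.3 / 0.6 / 1.0 |
|---|---|---|---|
| 10% / 10% | 0.70 | 0.698 | 0.698 / 0.698 / 0.699 |
| 5% / 10% | 1.00 | 0.997 | 0.991 / 0.983 / 0.975 |
| 5% / 10% | 0.70 | 0.697 | 0.693 / 0.689 / 0.684 |
| 10% / 5% | 0.70 | 0.697 | 0.703 / 0.707 / 0.714 |

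With 10% / 5% loss and a true HR of 1.00, the SAP rule gives 1.004 / 1.009 / 1.018. With equal 10% loss it adds 4 to 15 events to 296 and raises the overall rate from 8.8 to 8.9–9.2 per 100 patient-years.

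A second simulation assumed non-fatal first events at 6% and deaths at 3.5% per year, with every later death found. Equal loss gave no shift. Loss of 4% against 2% per year (active against placebo) turned a true 1.00 into 1.016, and 5% against 2% into about 1.025.

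For scale, the standard error of the log HR at 282 events is 2/√282 = 0.119. A shift to 1.025 is ln(1.025)/0.119 = 0.21 standard errors, and to 1.016 it is 0.13.

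**5. The two one-year analyses.**

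| | Table 3 | 3.2.2 |
|---|---|---|
| Events | all components | deaths only |
| Clock | date of occurrence | date of identification |
| Reference contact | last with all components assessed | most recent study contact |

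- A death one month after last contact, found by an NDI search two years later, is kept by Table 3 and censored by 3.2.2.
- An adjudicated MI 18 months after last contact is removed by Table 3 and kept by 3.2.2.

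Neither version is symmetric, because both keep some events after last contact. In the null case with 5% / 10% loss and f = 1.0, allowing events up to a year after last contact gives 0.986. That lies about halfway between 0.975 and 0.997, so about half of the shift remains.

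**The case against.** **The late-event reading is not certain.** A reader might take it as settled that a patient lost at year 2 who dies at year 4 is a primary event. The SAP does not say so. The opening sentence of 3.1.1 limits events to planned visits and calls, and only the all-cause mortality row expressly adds NDI deaths. This stands: the text must be reconciled, and f = 1.0 is a ceiling.

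**There is no bias without an added assumption.** The trial is double-blind and the documents report no difference in loss. The 5% per year in Protocol 9.2 combines withdrawal with loss, and events after withdrawal are excluded, so withdrawals cannot feed this mechanism. The second simulation gave type I error of 5.6% against 4.6% with a symmetric rule. Its Monte Carlo error is about 0.28 points, and 4.6% is itself below nominal. This also stands.

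**A literal single cut-off would delete real deaths.** A death always follows the patient's own last contact. At 6% and 3.5% per year, deaths are 3.5/9.5 = 37% of first events. If only patient contacts counted, a rule keeping events on or before the last assessed date would drop about 40% of primary events. Even if a proxy call always followed on schedule, it would drop about 4% with no loss at all. This decides against replacing the primary rule.

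**Other checks exist.** The event rule is a stated choice, modelled on TACT. The SAP also imputes events for withdrawn and lost patients, and uses a common NDI date for mortality. But imputation addresses events that were never observed, and the NDI date serves mortality only. Neither tests this asymmetry in the primary composite.

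**Conclusion.** The plan is internally inconsistent on three points: ICF expiration is missing from both censoring minima, events after last contact have a different limit from time at risk, and the one-year sensitivity analysis has two definitions. The first and third follow from the text alone. The second rests on the event column and the sensitivity row, against the opening sentence of 3.1.1.

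The numerical effect is small. The ICF gap was not simulated. Late events raise absolute rates in both arms. The HR shift of roughly 0.4–2.5% depends wholly on assumed differences in loss and on the assumed ascertainment. It goes toward benefit if placebo loses more patients and away from it if the active arm does.

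A reader might infer that the primary hazard ratio is biased, or that type I error is materially inflated. The documents do not support that: they give no loss by arm and no count of late-found events, and with equal loss the shift is nil. The case is for correcting the rules, not for replacing the primary analysis.

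**What to change.** 1. In SAP Table 3, add ICF expiration to both minima: min(consent withdrawal, ICF expiration, last contact at which event status was assessed). Carry this into the rows for recurrent events and the secondary composite.
2. Reconcile the opening sentence of 3.1.1 with the event column, stating whether adjudicated events found outside planned visits and calls count in the primary endpoint.
3. Make 3.2.2 match Table 3: one event set, one clock, one definition of the reference contact.
4. Add a sensitivity analysis with a single cut-off for events and censoring. Keep a death that a proxy reports at a scheduled contact, or that occurs before the next scheduled contact, so that genuine deaths are not dropped.
5. Keep the rule of counting all identified events as primary. Report, by arm, loss to follow-up and the number of primary events dated after last contact, so that the size of the effect can be seen.

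The cost is SAP wording and one more analysis. That analysis will contain slightly fewer events. With equal 10% loss, the events after last contact would be about 4 of 300 (1%) to 15 of 311 (5%), and the allowance for deaths would retain some of these.

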1.1 Study Design

The Trial to Assess Chelation Therapy 2 (TACT2) is a randomized, double blinded, placebo-controlled 2x2 factorial clinical trial. The study treatments are edetate disodium-based chelation (weekly infusion for 40 weeks) and high-dose oral multivitamins and multi-minerals (OMVM) (twice daily for up to 5 years). Subjects with diabetes mellitus with a prior myocardial infarction (MI) are recruited from participating sites in the US and Canada and randomized in a 1:1:1:1 fashion to 4 groups:

- i. Active chelation + active OMVM
- ii. Active chelation + placebo OMVM
- iii. Placebo chelation + active OMVM
- iv. Placebo chelation + placebo OMVM.

Patients will be followed for clinical events until the earlier of database lock or five years from randomization. Clinical outcomes will be collected by study sites at each infusion visit and by the DCRI Call Center at month 6 and 12, and every 4 months afterwards with the last assessment at month 60.

TACT2 is an event driven trial with a plan to continue until at least 282 primary endpoint events are identified. The original planned sample size was 1200 participants. The sample size was later modified to 1100. The final enrollment is 1000, but with an increased follow-up time to preserve statistical power. More details on sample size and power calculation are included later in the SAP.

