2.2 Data Sources

The data used for analysis will come from 5 sources: the randomization data from the Interactive Voice/Web System (IXRS), the e-CRF data collected by the iMedidata Rave electronic data capture system (RAVE), the adjudicated endpoint data from the clinical events committee database (CEC), the site-level information stored in the Clinical Trial Management System (CTMS) database, and the CDC National Death Index (NDI).

Masked-source NDI search results will be used to focus a search for supporting clinical and other documentation. If supporting documentation is obtained, the data will be submitted to the CEC process prior to being used in the analysis. If needed, a Mortality Review Committee will be assigned to classify potential death events when there are insufficient/incomplete or contradictory NDI and/or Call Center data to make a reliable determination. Additional details will be described in a separate charter.

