2.4 Disposition of Participants

Disposition of participants (number randomized, number who received treatment, number of infusions received per patient, number of withdrawals and dropouts from the study, number lost to follow-up, length of follow-up, time since last contact, number unmasked) will be summarized by active chelation vs placebo chelation groups using a CONSORT flow diagram and subject disposition table.

Lost to follow-up among alive and non-withdrawn participants will be reported in the CONSORT diagram as described above. The number of participants lost to follow-up with a primary endpoint will be included in the total and also reported separately. Participants alive and not withdrawn or lost to follow-up will be defined as completing the study.

The definition for lost to follow-up will be:

No contact within 12 months of the end of study. End of study is defined as the 5-year informed consent expiration date or administrative end of study date (June 30, 2023). Last contact is defined as the last known alive date.

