3.3.2 Time to Event Analysis of the Secondary Endpoints

The analyses for the time to the first occurrence of secondary endpoints (1) time to the first occurrence of the composite of cardiovascular mortality, MI, or stroke; 2) time to all-cause

mortality) will be performed in the same manner as the primary analysis in Section 4.1, replacing the primary composite endpoint with secondary endpoints.

Competing risk of non-CV death or undetermined death will be taken into account for the secondary composite endpoint (time to the first occurrence of the composite of cardiovascular mortality, MI, or stroke). Follow-up will be censored at the time of non-CV or undetermined death if there is no prior composite event. For this endpoint, the treatment effect will be presented as a cause-specific hazard ratio.

All deaths post-randomization will be included in the secondary all-cause mortality endpoint. For this endpoint, a death date after withdrawal of consent or ICF expiration (obtained from public data sources) is considered an event.

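### The step-2 mortality test counts deaths after contact has ended but censors survivors at last contact, so late follow-up time comes almost only from participants who die

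*SAP*

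**What the plan says.** **Deaths.** The all-cause mortality row of SAP Table 3 (3.1.1) includes adjudicated deaths found through the National Death Index (NDI), and "A death date after withdrawn consent or ICF expiration (obtained from public data source) is considered an event". SAP 3.3.2 repeats the rule: "All deaths post-randomization will be included in the secondary all-cause mortality endpoint". Neither place gives a closing date. Late deaths are vetted: SAP 2.2 uses NDI results to direct a search for documents, and "If supporting documentation is obtained, the data will be submitted to the CEC process prior to being used in the analysis".

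**Survivors.** The same row states "Censoring date = (date last known alive". That date comes from infusion visits or Call Center contacts, with one possible later source, the "last alive date from Call Center where death status was assessed". A negative NDI search adds no survivor time.

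**End of contact.** Under SAP 1.1 the Call Center assesses at months 6 and 12 and "every 4 months afterwards with the last assessment at month 60". SAP 2.4 adds: "End of study is defined as the 5-year informed consent expiration date or administrative end of study date (June 30, 2023".

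**Place in the plan.** SAP 3.2.1 makes mortality step 2 of the testing hierarchy and calls its censoring conservative, without defining the term. SAP 3.3.3 and Table 3 also prespecify a version that censors all survivors at a common NDI date. It is a sensitivity analysis, and its date is when NDI results were assessed, not the date through which deaths are complete.

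**The concern.** A valid risk set at time *t* holds everyone who would be seen to die at *t* if they died then, whatever happens later. Here, whether a participant stays in the risk set after last contact depends on whether they later die. Those who die stay until death; those who live leave at last contact.

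The SAP avoids this for the primary endpoint, where events after withdrawal or consent expiry are excluded, so events and censoring share one window. Only the mortality row mixes a wide window for deaths with a narrow one for survivors.

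Three things are at stake:
- absolute mortality and late Kaplan-Meier curves, in both arms;
- some power at step 2, where a miss blocks formal testing of steps 3 and 4;
- the hazard ratio itself, if the arms lose contact at different rates.

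**Working it through.** **The plan's own figure.** The SAP's 282 primary events (HR 0.70, two-sided 0.05, 85% power) reproduce: 4(1.96 + 1.036)² / (ln 0.70)² = 282.3. The documents give no death count or power for mortality, so the rest rests on assumptions.

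**Inputs from the documents.** 1000 participants, 1:1 for chelation; accrual over 4.25 years and 2.5 years of minimum follow-up; 5-year consent limit; end of study June 30, 2023; about 5% loss per year (Protocol 9.2).

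**Assumed.** Uniform accrual, placebo mortality 4% per year, true HR 0.70 (active 2.8% per year), and full capture of deaths to June 30, 2023, unless stated.

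**Hand calculation, no loss.** Potential follow-up *t* is uniform on 2.5 to 6.75 years.
- Deaths to June 30, 2023: 500 × mean of (1 − e^(−λt)) gives 83.9 placebo and 60.5 active, total 144.
- Deaths by min(*t*, 5): 78.2 and 56.2, total 134. So about 10 deaths fall after year 5, of which 83.9 − 78.2 ≈ 5.8 are placebo.
- Placebo participants alive at year 5 with calendar time still to run: 500 × (1.75/4.25) × e^(−0.20) ≈ 169. Under Table 3 only the 5.8 who die stay in the risk set, unless a survivor has a later alive date.
- About 4.7 of the 5.8 die by year 6, leaving 1.03. With simulated 5-year mortality of 18.6%, Kaplan-Meier mortality at 6 years is 1 − 0.814 × (1.03/5.76) ≈ 85%. The true value is 1 − e^(−0.24) = 21.3%.

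**Simulation** (Cox and Kaplan-Meier, 10,000 replicates; contact weekly to week 40, then months 12, 16, … 60). *Calendar* means deaths to June 30, 2023, with everyone else censored there. *Active* means deaths and censoring both limited to the earliest of loss, 5 years and June 30, 2023.

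| True HR 0.70 | Table 3 HR | Power: Table 3 | Calendar | Active | Placebo 5-y mortality, Table 3 (true 18.1%) |
|---|---|---|---|---|---|
| No loss | 0.71 | 51% | 57% | 53% | 18.6% |
| 5%/yr loss, both arms | 0.71 | 51% | 57% | 50% | 20.9% |

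The power formula Φ(½√d × |ln 0.70| − 1.96) agrees for the common cut-offs: 57% at d = 144, 54% at 134 and 50% at 121 (active deaths with 5%/yr loss). With no loss, null two-sided error under Table 3 is 5.1%, and 4-year placebo mortality reads 15.0% against a true 14.8%.

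**A second death rate.** Protocol Table 1 gives a 43% mortality reduction and a 5-year NNT of 12 in the earlier trial's diabetic subgroup. Solving S^0.57 − S = 1/12 gives S = 0.7925, or −ln(0.7925)/5 = 4.65% per year. With 5%/yr loss in both arms (3,000 runs, null), about 30 of 192 deaths fall after contact ends. The estimated death rate is 5.62 per 100 patient-years against 4.65, or 21% too high; the null HR is 1.00 and the error 5.0%. At true HR 0.70, Table 3 gives 0.71 with 57% power, against 63% with a common date.

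**Unequal loss (hypothetical, null; placebo versus active).**
- 5% vs 8% per year: HR 1.06.
- 6% vs 4% per year: HR 0.96, with 4.3% false positives favouring chelation instead of 2.5%.
- Overall dropout 5% vs 10%: 1.02; 10% vs 5%: 0.98.

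**Incomplete capture** of post-contact deaths at 100/90/75/50% (null, 5% vs 8% per year):
- Table 3: 1.06/1.06/1.05/1.04
- Calendar: 1.00/1.00/0.99/0.97
- Active: 1.00 throughout

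**The case against.** The best defence is that the test hardly moves under equal contact, and the trial is double-blind. This is right: the HR shift is about 0.01, type I error holds, and Table 3 is no worse than active follow-up when loss is 5% per year in both arms.

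The larger shifts are hypothetical. Loss of 5% vs 8% per year would mean about 19% vs 29% cumulatively (mean of 1 − e^(−w·min(t,5)) over the accrual above, ignoring deaths). The SAP's simulations use 5 to 10% overall; if that is cumulative, a 5% vs 10% split moves the null HR only to 1.02 or 0.98. Step 2 is also reached only after a significant primary result.

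The 85% figure is the extreme case. If 25% or 50% of survivors past year 5 had a later alive date, 6-year mortality would read 39% or 31%. The SAP does not ask for a 6-year estimate.

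Database lock, planned for October 2023 in SAP Appendix I, could be read as an implied limit on deaths. It would cap the deaths but would not restore survivor time.

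The symmetric analysis is prespecified, so a reader could compare the two. But it lies outside the hierarchy and cannot decide step 2 or open steps 3 and 4. The word *conservative* fits when loss is equal, since benefit is slightly attenuated. It fails if placebo loses more contact, because the HR then moves in favour of chelation.

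**Conclusion.** The concern holds. The asymmetry follows from the wording of Table 3 and needs no outside fact. It is at the low end of what should be fixed: the expected HR bias is small, but a confirmatory rule is wrong as written and cheap to correct.

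With equal loss, the cost is about 6 points of step-2 power against a calendar cut-off and inflated absolute mortality: 0.5 points at 5 years with no loss, 2.8 points at 5% loss per year. Kaplan-Meier estimates past year 5 are invalid in both arms. HR shifts of 4 to 6% need unequal contact, which the documents do not show.

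The death rate, accrual shape, loss by arm and capture are assumptions. Mortality of 3% or 5% per year leaves the HR at 0.71. Accrual that rises over time cuts late deaths to 3, with HR 0.70. Closing the NDI search in December 2022 or September 2023 gives 5 or 12 late deaths and HR 0.70 or 0.71.

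**What to change.** Make step 2 use one outcome-independent cut-off for deaths and survivors alike.

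1. Where death ascertainment is documented as complete (for example, NDI-covered participants), state the calendar date through which it is complete, not the date results were assessed. Count deaths to that date and censor everyone else there.
2. Where coverage is incomplete or unstated, which may apply to some participants since they are "recruited from participating sites in the US and Canada", count deaths only to the earliest of withdrawal or loss, 5-year consent expiry, and June 30, 2023. Censor survivors at the end of that same window. Date loss by one pre-set rule, such as the first missed scheduled contact; this gives null HRs of 0.994 to 0.998 at 5% vs 8% per year.
3. If completeness cannot be confirmed before unblinding, use rule 2 for everyone.
4. Keep the last-known-alive version as a sensitivity analysis, define or drop *conservative*, and show no Kaplan-Meier mortality past the common cut-off (year 5 for the last-known-alive and active-follow-up versions).

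With 20% of participants assumed outside NDI coverage and 5% vs 8% loss per year, this mixed rule gives HR 1.00 under the null, and 0.70 with 55% power at a true 0.70. Table 3 gives 1.05, and 0.75 with 39% power.

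**Cost.** SAP wording, derivation work and confirmation of NDI coverage; no new data. The calendar rule is biased if capture is incomplete and loss differs by arm: null 0.97, with 3.6% false positives favouring chelation, at 50% capture and 5% vs 8% per year. Active follow-up uses fewer deaths (134 vs 144 with no loss, 121 vs 144 at 5% per year), gains no power over Table 3 at equal 5% loss, and assumes loss is unrelated to prognosis.
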